- Eastern Cooperative Oncology Group(ECOG) performance status are 0 to 2.
- Expected survival over 3 months.
- Household registration is Guangdong Province.

Exclusion Criteria:

- Co-morbid conditions that affect survival: end stage congestive heart failure, unstable angina, myocardial infarction (within the past 6 weeks), and uncontrolled blood sugars of greater than 300 mg/dL, known chronic active hepatitis or cirrhosis.
- Glucose-6-phosphate dehydrogenase deficiency (G6PD) (a relative contraindication).

- Patients who are allergic to VitC.
- Patients with HIV and other infectious diseases.
- Patients who are taking anticoagulants and have coagulopathy;
- Combine dysfunction of important organs such as heart, lung, liver and kidney;
- Patients with impaired renal function (serum creatinine content > 1.2 mg/dL)
- Compromised liver function with evidence of Serum total bilirubin content, ALT and AST > 2 times normal reference value.
- Pregnant or lactating female.
- Smoking and alcohol abuse patients;
- Anti-infective treatment is required for systemic or localized serious infections;
- Patients with hyperuric acidosis (normal: 91-456 $\mu\text{mol} / 24\text{h}$ (8-40mg / 24h));
- Wilson's disease.
- Evidence of significant psychiatric disorder by history or examination that would prevent completion of the study or preclude informed consent.
- Any condition that impairs the patients' ability to swallow, which impairs drug absorption or drug kinetic parameters, including any kind of gastrointestinal resection or surgery;
- History of surgery of visceral organs within 6 weeks before the trial.

Study design:

Experimental period: 12.05.2018~31.12.2019

Method:

In experimental group:75 patients received a weekly intravenous Vitamin C injection (dose: 30 g / time, once a week, treatment termination when the disease progress is confirmed) in combination with daily TKI; In the control group:75 patients received only TKI daily. (dose: Osimertinib 80 mg/d, or Tarceva 150 mg/d, or Iressa 0.25 g/d.)

Outcome:

Primary outcome was PFS. Secondary outcome include: OS, QoL, tumor size.

Observations and assessments:

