To evaluate the effects of the above treatments on patient safety, tumor size, tumor markers, inflammatory factor levels, quality of life, progression-free survival and overall survival time. General information was collected before and after treatment, and the QoL was assessed on the quality of life questionnaire (QLQ-C30) scale. Chest CT enhancement, brain MRI, liver color Doppler ultrasound, adrenal gland ultrasound, blood test for liver and kidney function, blood and urine routine, tumor markers, tumor necrosis factor, interleukin-6 level were checked every month.

Statistical methods:

The effect of treatment on PFS, OS was analyzed by using Kaplan-Meier probability estimates. Comparison of tumor markers and immune factors was performed using t-test.

Key issues to be addressed:

To explore whether intravenous VitC can prolong resistance time of TKI on lung adenocarcinoma patients with EGFR mutations. To observe whether the combination treatment can benefit NSCLC patients.

Expected results:

Intravenous VitC in combination with TKI can significantly prolong the time of drug resistance, improve the quality of life, and have a positive effect on the prognosis of lung adenocarcinoma patients with EGFR mutations.

Safety measures and emergency plan:

Diarrhea, rash, liver dysfunction and other adverse reactions may occur during the treatment, but the above reactions will be eliminated under the doctor's treatment. If patients experience any discomfort during the study, or if there is a new change in the condition, or any unforeseen circumstances, whether or not related to treatment, patients should promptly notify their doctor, who will make a judgment and medical treatment. If the condition of the disease changes to a certain standard (if the condition progresses), the trial may be terminated earlier after discussion by the research group.

Reference

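### Symptomatic adverse events depend on patients reporting them, with weekly contact in the VitC arm against a monthly common schedule, so any between-arm comparison of these events is open to ascertainment bias

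*Combined protocol and SAP*

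**What the plan says.** Under Observations and assessments, the combined protocol and SAP puts safety first among the things to be evaluated: the "effects of the above treatments on patient safety". The treatments in question are the two arms.

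Under Safety measures and emergency plan, diarrhea, rash and liver dysfunction are named as possible reactions. The text then continues: "If patients experience any discomfort during the study, or if there is a new change in the condition", or in any unforeseen circumstance, "patients should promptly notify their doctor", who then judges and treats the problem. No scheduled questioning, adverse-event form, grading scale or recall period is described. The quality-of-life questionnaire is not presented as a source of adverse events.

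Under Study design, Method, the experimental arm has "a weekly intravenous Vitamin C injection" until progression is confirmed, with daily TKI. The control arm has daily TKI only, and no matching visit is described.

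Imaging and laboratory tests, including liver and kidney function and routine blood and urine, "were checked every month", with no arm singled out.

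Safety is not among the primary and secondary outcomes, and Statistical methods contains no adverse-event analysis.

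**The concern.** If a symptom enters the record only when the patient mentions it, the number recorded depends on how often the patient meets someone to tell. Here that frequency differs between the arms by design. A higher count of diarrhea or rash in the VitC arm could be added toxicity or added contact. The same mechanism could hide a benefit: if VitC truly reduced TKI side effects, fuller recording in that arm could cancel the reduction.

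This matters because safety is a stated aim, and because Key issues to be addressed asks whether the combination benefits patients, to which tolerability is relevant. Events never recorded in the control arm cannot be recovered at analysis, so the collection method has to be set beforehand.

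**Working it through.** The plan gives no adverse-event rate and no figure for completeness of reporting, so there is nothing to reproduce. The check is of contact frequency, followed by an illustration on stated assumptions.

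**1. Contact (from Study design, and Observations and assessments).** Weekly infusions are about 52 a year and monthly assessments are 12, so 52/12 = 4.3. If the monthly assessment is a separate visit from the infusions, the ratio is (52 + 12)/12 = 5.3. Weekly contact with staff is inferred from the infusion, and it applies until progression.

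**2. Which events are exposed.**

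| Event type | How it is found | Same in both arms? |
|---|---|---|
| Liver dysfunction, other laboratory events | Monthly tests | Yes, no arm singled out |
| Diarrhea, rash | Patient tells doctor | Contact weekly vs monthly |
| Infusion complaints (not named in the plan) | Patient tells doctor | Arise in the VitC arm only |

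**3. Illustrative size.** Assumptions, none of them from the documents:
- True event rates are equal in the two arms.
- A share q of events is notified promptly in both arms.
- The rest can be reported only at the next contact, and the chance of reporting falls exponentially with the wait, with mean recall time τ.
- Events are brief and fall evenly over the contact interval L (7 days, or 365.25/12 = 30.44 days).

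Share captured at contacts: c(L) = (τ/L)(1 − exp(−L/τ)).

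Apparent rate ratio: [q + (1 − q)c(7)] / [q + (1 − q)c(30.44)].

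For τ = 14 days:
- VitC: (14/7)(1 − exp(−0.5)) = 2 × 0.3935 = 0.787.
- Control: (14/30.44)(1 − exp(−2.174)) = 0.460 × 0.886 = 0.408.
- With q = 0: 0.787/0.408 = 1.93.
- With q = 0.5: (0.5 + 0.5 × 0.787)/(0.5 + 0.5 × 0.408) = 0.893/0.704 = 1.27.

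| τ (days) | c, VitC | c, control | Ratio, q = 0 | q = 0.5 | q = 0.8 | q = 1 |
|---|---|---|---|---|---|---|
| 14 | 79% | 41% | 1.93 | 1.27 | 1.09 | 1.00 |
| 30 | 89% | 63% | 1.42 | 1.16 | 1.06 | 1.00 |
| 60 | 94% | 78% | 1.20 | 1.09 | 1.03 | 1.00 |

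**4. What this could do to a simple test.** Suppose 90% of affected patients are recorded in the VitC arm and 70% in the control arm, close to the case τ = 14, q = 0.5. With 75 per arm (Study design) and an assumed true rate of 50% in both, the observed rates are 45% and 35%. For a two-sided 5% test of two proportions:
- Standard error under no difference: √(2 × 0.40 × 0.60/75) = 0.0800.
- Standard error under the observed rates: √((0.45 × 0.55 + 0.35 × 0.65)/75) = 0.0796.
- Chance of a significant result: Φ((0.10 − 1.96 × 0.0800)/0.0796) = Φ(−0.71) = 24%, against 5% if recording were equal.

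At true rates of 30% and 70% the chance is 13.5% and 41%. The plan names no such test; this shows only what an ordinary comparison would face.

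**The case against.** The strongest reply is that the sentence on notifying the doctor is a care instruction, not a data-collection method, and that the plan specifies no adverse-event comparison. A reader might infer that the plan commits to comparing safety between arms from volunteered reports. It does not say so: safety is not a listed outcome and has no analysis. What remains is that evaluating the treatments' effects on safety is an aim, and patient notification is the only route described for symptoms. Any comparison made in pursuit of that aim would rest on it.

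Second, the instruction asks for prompt notification in both arms, whether or not the problem is related to treatment, and without waiting for a visit. With full compliance the visit interval is irrelevant and the ratio is 1.0. This stands, and it is why the range starts there. Likewise, a rash or diarrhea still present at the monthly visit would not be lost as the model supposes.

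Third, the monthly laboratory tests seek liver, kidney, blood and urine abnormalities with no arm singled out. This also stands. It would be wrong to infer that the trial can say nothing about added toxicity; the exposure is confined to symptomatic events.

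Finally, a reader might infer that weekly contact also moves progression dates through extra scans in the VitC arm. The documents mention no unscheduled scans, and chest CT and brain MRI are monthly with no arm singled out. They do not support that extension to PFS.

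**Conclusion.** The point holds for symptomatic adverse events. The plan aims to evaluate safety, describes no structured collection of symptoms, and gives the arms unequal contact, about 4.3 to 1. A between-arm comparison of such events is therefore open to ascertainment bias, most likely towards more recorded events in the VitC arm. That it is in fact distorted, or by how much, cannot be established from the documents.

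On the assumed model, the apparent rate ratio with no true difference lies between 1.0 and about 1.9. It reaches the upper end only if nothing is notified between visits and mean recall is 14 days; with half of events notified promptly it is 1.09 to 1.27. The recall times, notification shares and brief-event assumption are illustrative. The point does not touch the primary PFS analysis, but it should be settled before data are collected.

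**What to change.** At the existing monthly assessment in both arms, ask about the same fixed list of adverse events over the past month. Use the same form and CTCAE grading, and include the reactions the plan already names. Record the visit at which each event was found.

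State in Statistical methods that the between-arm comparison of symptomatic events uses these monthly records. Report all events noted at infusion visits in a separate table. No dose, treatment schedule or treatment rule changes.

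The cost is one form, a comparative table, a separate infusion-visit table, and a few more minutes per monthly visit. The comparative table alone may under-represent events seen only around infusions, so the separate table is a necessary part of the change. The form equalises when and how patients are asked; it does not remove any difference in expectation between patients who receive infusions and those who do not.
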